10.2 Subject Accountability

The number of subjects enrolled will be tabulated by countries and investigator sites overall and by treatment group (when applicable). Subject disposition (including the number screened, enrolled, treated, ended treatment, ended radiographic follow-up, and that completed the safety follow-up visit) will be summarized separately for all enrolled subjects in phase 1b. Subject accountability will be tabulated by respective treatment group when applicable. Reasons for not receiving treatment, for ending treatment, endpoint radiographic follow-up, and not completing the 30-day safety follow-up visit will be provided.

10.3 Important Protocol Deviations

Important Protocol Deviations (IPDs) categories are defined by the study team before the first subject's visit and updated during the IPD reviews throughout the study prior to database lock. These definitions of IPD categories, sub-category codes, and descriptions will be used during the course of the study.

Eligibility deviations are defined in the protocol. Eligibility deviations that are defined as IPDs will be summarized in both the IPD and Eligibility Deviation table and IPD and Eligibility Deviation listings.

10.4 Demographic and Baseline Characteristics

Summary statistics of the following demographic and baseline characteristics will be tabulated using the SAS for phase 1b of the study.

- Region (South America vs North America vs EU vs Asia vs Other for phase 1b; South America vs North America vs EU vs Japan vs Other Asia vs Other for phase 3)
- Age at baseline: < 50, ≥ 50; < 65, ≥ 65; < 75, ≥ 75 years
- Sex (female vs. male)
- Prior smoking (never vs former vs current)
- HSV-1 serostatus (positive vs negative)
- The sum of diameters of target lesions
- Weight loss > 5% in the previous 6 months

- Primary tumor site (oral cavity vs oropharynx vs hypopharynx vs. larynx)
- Brain metastasis status (baseline brain metastasis vs no baseline brain metastasis)
- Prior radiotherapy for treatment of SCCHN
- Extent of disease (metastatic vs locoregionally recurrent)
- Prior lines of therapy in recurrent/metastatic setting (0, 1 or 2)
- PD-L1 status at baseline (positive versus not positive)
- CD8+ T cell density
- HPV (HPV- negative vs HPV-positive vs unknown)
- ECOG performance status (0 vs 1)
- Maximum blinded investigational product total volume per treatment administration > 4 mL at highest concentration (yes, no)

10.5 Efficacy Analyses

10.5.1 Analyses of Primary Efficacy Endpoint(s)

10.5.1.1 Phase 1b

The subject incidence of DLT will be summarized using the DLT Analysis Set.

10.5.2 Analyses of Secondary Efficacy Endpoints

10.5.2.1 Phase 1b

The primary analysis of efficacy for the phase 1b will be based on the EAS, with secondary analysis based on the FAS overall and excluding subjects in the EAS. All endpoints of the phase 1b will be descriptively analyzed.

The main efficacy endpoint in the phase 1b for the phase 3 decision will be the iORR with or without confirmation of response. Given the observed iORR in the Efficacy Analysis Set, the Bayesian posterior probability will be calculated that the true combination iORR exceeds the expected ORR for pembrolizumab by an absolute amount (δ). The expected iORR for pembrolizumab in the study population with 9 weeks minimum potential follow-up is approximately 11% and will be represented by a $\text{beta}(2.2, 17.8)$ distribution with mean 0.11 and precision 20.0. The iORR for the combination will be represented by a $\text{beta}(0.2, 1.8)$ distribution with mean 0.11 and precision 2.0. Given the observed iORR, the posterior probability will be calculated for a δ increase from 0% to 30% in 5% increments as well as a 90% credible region for δ (see [REDACTED]).

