10.4.5 Primary Analysis

10.4.5.1 Primary Analysis Phase 1b

For the phase 1b part of the study, the primary analysis will occur when the last subject enrolled has had the opportunity to complete the 9-week response assessment.

10.4.5.2 Primary Analysis Phase 3

For the phase 3 part of the study, the timing for the primary analysis of OS will be event-driven based on the FAS(G). The event goal for OS is 336. Detailed approximate timings of the analyses are shown in [Table 9](#).

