Appendix D. Radiological Guidance for Assessment of Disease Response

Initially developed in 2000 and modified in 2009, RECIST guidelines provide a standard approach to solid tumor measurement and definitions for objective assessment of change in tumor size in adult and pediatric cancer clinical trials. More recently, however, to account for the unique tumor response characteristics seen with treatment with immunotherapeutic agents, standard RECIST v1.1 will be adapted (irRECIST) to assess tumor responses in this study for treatment decisions only. Immunotherapeutic agents such as pembrolizumab and talimogene laherparepvec may produce antitumor effects by potentiating endogenous cancer-specific immune responses. The response patterns seen with such an approach may extend beyond the typical time course of responses seen with cytotoxic agents, and can manifest a clinical response after an initial increase in tumor burden or even the appearance of new lesions. Standard RECIST v1.1 therefore may not be the optimal method for response assessment of immunotherapeutic agents. Immune-related RECIST (irRECIST) is RECIST v1.1 adapted to account for the unique tumor response seen with immuno-therapeutics. irRECIST will be used by local site investigators to assess tumor response and progression, and make treatment decisions. Adaptations for irRECIST include the following:

- For initial progressive disease (PD), tumor assessment should be repeated ≥ 4 weeks later in order to confirm PD with the option of continuing treatment per below while awaiting radiologic confirmation of progression.
- If repeat imaging shows $< 20\%$ tumor burden compared to nadir, stable or improved previous new lesion (if identified as cause for initial PD), and stable/improved non-target disease (if identified as cause for initial PD), treatment may be continued/resumed.
- In determining whether or not the tumor burden has increased or decreased, all target lesions as well as non-target lesions should be considered.

Note: For phase 3 only, investigators will also be asked to assess and document tumor response per standard RECIST v1.1. However, RECIST v1.1 response assessment should NOT be used in treatment decisions.

Method of Measurement of Tumor Lesions:

CT scans (or MRI):

Computed tomography (CT) scans by contrast-enhanced or spiral scan (or magnetic resonance imaging [MRI] scan) will be performed to evaluate tumor response for visceral

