iBOR	best overall response (per irRECIST)
iCR	complete response (per irRECIST)

Abbreviation or Term	Definition/Explanation
iCRR	complete response rate (per irRECIST)
iDCR	disease control rate (per irRECIST)
iDOR	duration of response (per irRECIST)
iORR	objective response rate (per irRECIST)
iPD	progressive disease (per irRECIST)
iPFS	progression-free survival (per irRECIST)
iPR	partial response (per irRECIST)
irRECIST	Immune-related Response Evaluation Criteria in Solid Tumors (RECIST)
iSD	stable disease (per irRECIST)
iUE	unable to evaluate (per irRECIST)
IV	intravenous
IVR	Interactive Voice Response
KM	Kaplan-Meier
L-CR	lesion complete response
L-ORR	lesion objective response rate
L-PR	lesion partial response
LSE(G)	global last subject enrolled
MRI	magnetic resonance imaging
ND	not done
ORR	objective response rate (per RECIST v1.1)
OS	overall survival
PD	progressive disease (per RECIST v1.1)
PD-L1	programmed cell death-1 ligand 1
PFS	progression-free survival (per RECIST v1.1)
PFU	plaque-forming unit
PK	pharmacokinetics
PR	partial response
qPCR	quantitative polymerase chain reaction
rcd	rapid clinical deterioration
RECIST	Response Evaluation Criteria in Solid Tumor
SAE	serious adverse event
SAP	Statistical Analysis Plan
SAS	Safety Analysis Set
SCCHN	squamous cell carcinoma of the head and neck
SD	stable disease (per RECIST v1.1)

Abbreviation or Term	Definition/Explanation
UE	unable to evaluate (per RECIST v1.1)
WHO DRUG	World Health Organization Drug

1. Introduction

The purpose of this Statistical Analysis Plan (SAP) is to provide details of the statistical analyses that have been outlined within the protocol amendment #4 for Talimogene Laherparepvec Study 20130232 dated 11 May 2018. The scope of this plan includes the primary analysis, follow-up analysis, and final analysis of the phase 1b part of the study that are planned and will be executed by the Biostatistics department unless otherwise specified.

The clinical study report (CSR) will be written based on the results of the primary completion analysis, follow-up analysis, and final analysis of phase 1b. Data collected and analyzed in Amgen-owned databases and systems will adhere to approved Data Element Standards and International Case Report Form (CRF) Standards established by Biomedical Data Stewardship Governance (BDSG).

2. Objectives

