3.1.3 Follow-Up

3.1.3.1 Follow-Up Analysis for Phase 1b

For the phase 1b part of the study, the primary analysis will be repeated 1 year after the last subject enrolled.

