An event of interest (EOI) is a noteworthy treatment-emergent adverse event for **talimogene laherparepvec** that may warrant careful monitoring. It could be serious or non-serious, and could include events that might be potential precursors or prodromes for more serious medical conditions in susceptible individuals ([Council for International Organizations of Medical Sciences \(CIOMS\) VI, 2005](#)). [REDACTED]

[REDACTED]. The set of EOIs to be evaluated will be identified at the time of analysis based on the current

product-specific standard MedDRA queries or **Amgen MedDRA Queries** maintained by Amgen Pharmacovigilance Operations.

Investigational product (IP)

Investigational product (IP) refers to talimogene laherparepvec (also known as “Amgen IP”) and pembrolizumab (also known as “non-Amgen IP”).

Lesion complete response (L-CR)

Lesion complete response (L-CR) applies only to measurable lesions (baseline) and is defined as complete disappearance of a lesion with confirmation by a repeat consecutive assessment no less than 4 weeks (28 days) from the date first documented. A lesion will be censored for L-CR after the start of non-study anticancer therapy, if it merges with another lesion or it is resected (except if it is completely resected and pathology indicates absence of malignant cells).

Lesion objective response rate (L-ORR)

Lesion objective response rate (L-ORR) is defined as the incidence among a set of lesions analyzed of L-CR or L-PR. Lesions without a follow-up assessment will be regarded as a non-responding lesion.

Lesion partial response (L-PR)

Lesion partial response applies only to measurable lesions (baseline) and is defined as $\geq 30\%$ decrease in lesion length (ie, longest diameter for non-nodal, shortest axis for nodal) relative to baseline with confirmation by a repeat consecutive assessment no less than 4 weeks (28 days) from the date first documented. A lesion will be censored for L-PR after the start of non-study anticancer therapy, if it merges with another lesion or it is resected (except if it is completely resected and pathology indicates absence of malignant cells).

Objective response rate (iORR) per irRECIST

iORR is defined as the incidence of an iBOR of iCR or iPR per irRECIST among a set of subjects analyzed. Subjects with an iCR or iPR will be defined as responders. Subjects who do not have any follow-up tumor assessments will be regarded as non-responders per irRECIST.

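### Does the 9-week pembrolizumab prior in SAP 10.5.2.1 need an explicit data cut, given that the same plan also covers the 1-year and final analyses?

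*SAP*

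**What the plan says.** SAP 10.5.2.1 has two paragraphs. The first makes the Efficacy Analysis Set (EAS) primary for phase 1b efficacy and says that all endpoints are analysed descriptively. The second describes iORR, with or without confirmation, as "The main efficacy endpoint in the phase 1b for the phase 3 decision", and sets out a Bayesian posterior for the absolute gain over pembrolizumab. The benchmark is stated as follows: "The expected iORR for pembrolizumab in the study population with 9 weeks minimum potential follow-up is approximately 11" per cent. It is represented by beta(2.2, 17.8). The combination prior is beta(0.2, 1.8), with a stated mean of 0.11. No data cut is named, and the cross-reference that closes the paragraph is redacted.

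On timing, Protocol 10.4.5.1 says that for phase 1b "the primary analysis will occur when the last subject enrolled has had the opportunity to complete the 9-week response assessment". SAP 3.1.3.1 adds that "the primary analysis will be repeated 1 year after the last subject enrolled". SAP Section 1 says "The scope of this plan includes the primary analysis, follow-up analysis, and final analysis of the phase 1b part of the study" and that the study report "will be written based on the results of the primary completion analysis, follow-up analysis, and final analysis of phase 1b". SAP Section 11 records that the sponsor reviewed the phase 1b primary analysis and then decided not to start phase 3. SAP 10.5.5 allows the Bayesian analysis to be repeated with a different pembrolizumab prior or with new external results.

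**The concern.** The benchmark belongs to a minimum of 9 weeks of follow-up, while the SAP's scope runs to 1 year and beyond. SAP Section 6 states that "iORR is defined as the incidence of an iBOR of iCR or iPR per irRECIST among a set of subjects analyzed". Because iBOR is the best response recorded, under a fixed confirmation rule the number of responders can only stay level or rise as scans accumulate. On the 9-weekly schedule a subject has up to five scheduled scans by week 52 (weeks 9, 18, 27, 36 and 45).

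Protocol Appendix D expects late responses with immunotherapies, pembrolizumab included: "The response patterns seen with such an approach may extend beyond the typical time course of responses seen with cytotoxic agents". If the pembrolizumab rate also grows with follow-up, a later posterior against a fixed 11% would credit the combination with responses that pembrolizumab alone might have produced. At stake would be one figure in the study report that looks better than it should.

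**Working it through.** **Inputs.** Priors from SAP 10.5.2.1. Expected EAS size of about 27 from Protocol 10.2.1. No document gives a later pembrolizumab rate for this population, so comparator rates above 11% are assumptions, taken over 11% to 20%. The upper end is the control rate assumed for phase 3 in Protocol 10.2.2 with 19 weeks minimum follow-up. That planning value does not isolate the effect of follow-up length. Precision is held at 20 throughout.

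**The plan's own figures.** A beta(a, b) distribution has mean a/(a+b) and precision a+b.
- Pembrolizumab: 2.2/(2.2+17.8) = 0.11, precision 20.0. Both agree with the text.
- Combination: 0.2/(0.2+1.8) = 0.10, precision 2.0. The stated mean is 0.11. Beta(0.22, 1.78) has mean 0.22/2.0 = 0.11 and rounds to the printed parameters at one decimal, so rounding is the likely cause. Exchanging the two priors moves the posterior by at most about 0.003 for 3 to 14 responders of 27 and gains of 0 to 30 points.

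**Sensitivity to the benchmark.** With x responders of 27, the combination rate has posterior beta(0.2+x, 28.8−x). The pembrolizumab rate is beta(20m, 20(1−m)) for prior mean m. For x = 6 the mean gain is 6.2/29 − m, that is 0.214 − m.

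| m | P(combination > pembrolizumab) | Mean gain, points |
|---|---|---|
| 11% | 0.85 | 10.4 |
| 13% | 0.80 | 8.4 |
| 15% | 0.73 | 6.4 |
| 20% | 0.56 | 1.4 |

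**No-benefit case, which isolates the mismatch.** Let both treatments have true rate r at the later cut, take x as binomial(27, r), and average the posterior over x.

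| r | 11% prior kept | Prior centred on r |
|---|---|---|
| 11% | 0.483 | 0.483 |
| 13% | 0.555 | 0.481 |
| 15% | 0.621 | 0.478 |
| 20% | 0.754 | 0.472 |

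The distortion is nil if the pembrolizumab rate does not move, about 0.07 at 13% (0.555 − 0.481) and about 0.28 at 20% (0.754 − 0.472). The chance of exceeding a fixed cutoff is a poorer measure. At r = 13% with a cutoff of 0.80 it is 13% with the 11% prior and 5% with the matched prior, but only because the matched posterior at 6/27 is 0.797. Moving the cutoff to 0.79 makes both 12.9%. The readable plan sets no cutoff.

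**Does the plan call for the later calculation?**
- Purpose: the Bayesian step is introduced as serving the phase 3 decision, and Protocol 10.2.1 gives the same reason.
- Data: the primary analysis is set at the last subject's 9-week assessment, which is the follow-up attached to the prior.
- Sequence: SAP Section 11 places the decision after that analysis.
- Structure: the descriptive analysis and the decision calculation are in separate paragraphs, and SAP 10.5.3.1 sends the exploratory response endpoints to the first paragraph only. Repeating the descriptive analysis at 1 year is a reasonable way to carry out the planned repeat.

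**The case for a change.** The best argument for a change is that the SAP post-dates the phase 3 decision, still says that the posterior will be calculated, and promises to repeat the primary analysis without exempting this step. Read literally, the repeat could include it. SAP 10.5.5 is optional, supplies no alternative prior and does not mention follow-up length. One sentence would settle the matter.

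Part of this stands: no readable sentence rules out a rerun. The argument from tense does not. The same SAP uses the future tense for work already finished, such as enrolment of the expansion cohort (3.1.1) and the DLT interim analyses (8.1.1). The redacted cross-reference directly after the calculation may also hold the missing detail, and text lost to redaction cannot be counted as a gap. As for SAP 10.5.5, showing the posterior over several pembrolizumab priors is the natural safeguard at a later cut, and that section already permits it.

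**Conclusion.** No change follows. At the 9-week cut the prior, the data and the purpose match, and there is no error. The mismatch would arise only if the decision calculation were rerun on later data, a step the plan does not state and whose purpose has lapsed. A statistician preparing the 1-year or final report would either leave it out or, under SAP 10.5.5, show it against other pembrolizumab rates and note the difference in follow-up.

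If it were rerun without that care, the expected posterior under no benefit would rise by between 0 and about 0.28, depending on an assumed later pembrolizumab rate of 11% to 20%, with 27 subjects and precision 20. That would affect a descriptive figure and no decision. The printed mean of the combination prior is a clerical slip worth at most about 0.003, so correcting it would gain nothing.

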10.5.3 Analyses of Exploratory Endpoints

10.5.3.1 Phase 1b

The exploratory analysis for Phase 1b for ORR, CRR, BOR, DCR, and DOR (response by investigator using modified RECIST v1.1) will be analyzed using the analysis methods described in **the first paragraph of Section 10.5.2.1** above, where applicable.

- Response rates in injected and uninjected lesions:
L-ORR and the incidence of L-PR and L-CR separately at the lesion level will be summarized by enrolled/randomized treatment for subjects in the EAS (phase 1b) and FAS(G)(phase 3) for the Injected Lesion Analysis Set and the Uninjected Lesion Analysis Set separately, and also for the corresponding evaluable analysis sets. Waterfall plots for the maximum percent decrease in the lesion diameter will also be provided. The number of subjects will be provided with at least one lesion in each analysis as well as the distribution of the number of lesions per subject. The subject incidence of an L-CR or L-PR and each individually will also be summarized separately for subjects with a lesion included in the Injected Lesion and Uninjected Lesion analysis sets and corresponding evaluable analysis sets.

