10.2 Sample Size Considerations

10.2.1 Sample Size Considerations for Phase 1b

In testing for the null hypothesis H_0 that the combination of talimogene laherparepvec and pembrolizumab has a DLT rate $\leq 10\%$ versus the alternative hypothesis (H_a) that the true DLT rate is $\geq 33\%$, the sample size goal is to have $\geq 80\%$ power for a 1-sided $\leq 10\%$ significance level test to reject H_0 when H_a is true ([Goldman AI, 1987](#)).

With up to 3 safety interim analyses, the sequential stopping rules shown in [Table 1 \(Section 3.1.1\)](#) gives 81.6% power for a 7.7% 1-sided significance level test. A maximum of 18 DLT-evaluable subjects will be enrolled. If > 18 subjects receive the combination they will contribute to the overall safety analysis, but only the first 18 DLT-evaluable will be considered in the decision to declare the combination safe. Subjects may be replaced if they are not evaluable for DLT to obtain 18 DLT-evaluable subjects (eg, a subject did not receive study treatment, or ended the study treatment before completion of DLT evaluation period for a reason other than experiencing a DLT). The null hypothesis may be accepted and the combination declared safe prior to 18 DLT-evaluable subjects if it can be definitively determined that the stopping rule will not be exceeded with additional subjects.

An expansion cohort of up to an additional 22 treated subjects will be enrolled so there will be 40 treated subjects in total. The decision to proceed to phase 3 will consider safety data in all treated subjects and efficacy among all treated subjects excluding those with locoregionally advanced disease with disease progression or recurrence < 3 months after prior platinum-containing curatively intended multimodal therapy. The efficacy analysis is expected to include approximately 27 subjects. The decision to proceed to phase 3 will consider, for example, long-term tolerability and minimum efficacy consistent with pembrolizumab monotherapy historical data.

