3.1.2 Tumor Response Assessment

For Phase 1b, conventional RECIST 1.1 ([Eisenhauer et al., 2009](#)), with the following modification, will be used by the investigator to determine eligibility:

- Increased total target lesions to a maximum of 10 (up to a maximum of 5 per organ)

A variation of RECIST 1.1, irRECIST, will be used by the investigator to assess tumor response and make treatment decisions, and to assess the secondary tumor response related endpoints in the phase 1b portion of the study.

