7.14 Lesion Analysis Sets

The Injected Lesion Analysis Set includes any target lesion that was ever injected and the Uninjected Lesion Analysis Set includes any target lesion that was never injected. The Injected Lesion Evaluable and Uninjected Lesion Evaluable analysis sets will include the corresponding subset of target lesions with at least one post-baseline measurement prior to a censoring event, ie, non-study anticancer therapy, merged with another lesion, or resection (except if it is completely resected and pathology indicates

absence of malignant cells). If a lesion splits, the sum of the length of the split lesions will be added together prior to analysis.

8. Interim Analysis and Early Stopping Guidelines

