9.6 Distributional Characteristics

All binary endpoints will be assumed to follow a binomial distribution. The KM estimates for the probability of time-to-event endpoints are based on non-parametric methods.

Time to event endpoints will be evaluated with the non-parametric log-rank test.

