10.1 General Principles

For the phase 1b part of the study, the DLT Analysis Set will be used to summarize the subject incidence of DLT and, unless specified otherwise, the SAS will be used for all analyses of safety. Safety may also be analyzed using the EAS. The primary analysis of efficacy for the phase 1b will be based on the EAS with secondary analyses based on the FAS overall and excluding subjects in the EAS.

In principle, summary statistics including mean, standard deviation, median, first and third quartiles, will be provided for continuous variables. Frequency and percentage will be summarized by treatment arm for binary and categorical variables. Proportions and the corresponding 95% confidence intervals will be based on normal approximations and

the treatment comparison will be based on a Cochran-Mantel-Haenszel test. Exact tests will be considered for subgroup analyses when the cell size is considered small.

Time to-event endpoints will be estimated using the KM method.

Descriptive statistics will be provided for efficacy, safety, talimogene laherparepvec DNA, and biomarker endpoints as appropriate

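### The SAP's default interval for proportions, if used for lesion-level response rates, ignores within-subject clustering and would be too narrow

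*SAP*

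**What the plan says.** - **Endpoint.** SAP Section 6 (Definitions): "Lesion objective response rate (L-ORR) is defined as the incidence among a set of lesions analyzed of L-CR or L-PR". The denominator is lesions, not subjects.
- **Which lesions.** SAP 7.14: "The Injected Lesion Analysis Set includes any target lesion that was ever injected". The uninjected set takes the target lesions never injected. SAP 3.1.2 allows up to 10 target lesions per phase 1b subject, 5 per organ, so several lesions from one subject can enter a set.
- **Analysis.** SAP 10.5.3.1: "L-ORR and the incidence of L-PR and L-CR separately at the lesion level will be summarized", for subjects in the Efficacy Analysis Set (EAS). The same bullet adds waterfall plots, the number of subjects with a lesion in each analysis, the distribution of lesion counts per subject, and the subject-level incidence of lesion response.
- **Default for proportions.** SAP 10.1: "Proportions and the corresponding 95% confidence intervals will be based on normal approximations". SAP 9.6: "All binary endpoints will be assumed to follow a binomial distribution".
- **Exceptions.** SAP 10.6.8 replaces the default with exact intervals for the qPCR proportions. The lesion-level rates have no such override. Neither document mentions a robust variance, GEE, a cluster bootstrap or any other allowance for within-subject correlation.
- **Status.** The endpoint is exploratory (SAP 4.1.3), and SAP 10.5.2.1 says: "All endpoints of the phase 1b will be descriptively analyzed".

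**The concern.** Lesions in one subject share a host, the same systemic pembrolizumab and the same scan schedule, so positive correlation between their responses is the natural expectation. A binomial normal-approximation interval counts each lesion as an independent trial. The lesion count then makes a trial of about 27 subjects look larger than it is, and the error bars on the injected and uninjected rates look tighter than the data support. The subject-level incidence that is also planned estimates a different quantity, so it does not correct a lesion-level interval.

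**Working it through.** The documents give no lesion-level rate, lesion count, interval width or ICC, so there is no stated figure to reproduce. The check asks how far the default interval would be off over a plausible range.

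**Inputs**
- Subjects (clusters): K = 27, from Protocol 10.2.1: "The efficacy analysis is expected to include approximately 27 subjects".
- Assumed: lesion response rate p = 0.25; m = 3 lesions per subject in the set analysed; ICC from 0 to 0.5.

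**Formulas**
- Default half-width = 1.96 × √(p(1 − p)/(K·m)) = 1.96 × √(0.25 × 0.75/81) = 9.4 percentage points.
- Design effect: DE = 1 + (m − 1) × ICC. The correct half-width is the default multiplied by √DE.
- Large-sample coverage of the default interval = 2Φ(1.96/√DE) − 1.
- Coverage was also simulated from a beta-binomial model (40,000 trials per scenario).

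| ICC | DE | √DE | Correct half-width (points) | Effective lesions, 81/DE | Large-sample coverage | Simulated coverage |
|---|---|---|---|---|---|---|
| 0 | 1.0 | 1.00 | 9.4 | 81 | 0.950 | 0.944 |
| 0.1 | 1.2 | 1.10 | 10.3 | 67.5 | 0.926 | 0.918 |
| 0.3 | 1.6 | 1.26 | 11.9 | 50.6 | 0.879 | 0.867 |
| 0.5 | 2.0 | 1.41 | 13.3 | 40.5 | 0.834 | 0.822 |

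The default standard error is understated by 1 − 1/√DE: 9%, 21% and 29% for ICC 0.1, 0.3 and 0.5. The ICC 0 row shows that, in this scenario, the normal approximation itself costs little (0.944 against 0.95). The rest of the loss is clustering.

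**Sensitivity**
- Lesions per subject (p = 0.25): with 2, coverage is 0.888 (ICC 0.3) or 0.862 (ICC 0.5); with 4, it is 0.824 or 0.758. With 1 lesion per subject DE = 1, so clustering has no effect.
- Rate (m = 3, ICC 0.3): about 0.86 at p = 0.20 and 0.85 at p = 0.30.
- Unequal counts of 1 to 10 lesions, mean 3 (p = 0.30, ICC 0.3): 0.78, worse than with equal counts.

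**Does the remedy work with so few clusters?** At p = 0.30 and ICC 0.3, a cluster-robust t interval on 26 degrees of freedom covers about 0.94 with equal counts of 3 and 0.92 with the unequal counts.

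**The case against.** The strongest reply is that the SAP may never produce such an interval. SAP 10.5.3.1 speaks only of summarizing. The interval rule comes from a general paragraph in 10.1 that is stated as a principle and also covers summaries by treatment arm and Cochran-Mantel-Haenszel comparisons, which cannot apply to a single-arm phase 1b. Where the SAP wants an interval for an exploratory proportion, as for qPCR, it says so on the spot, and the protocol synopsis ties the phase 1b response intervals to subject incidence. This stands in part. A reader might infer that the SAP commits to naive lesion-level intervals; the text does not go that far, so the point is conditional on intervals being given. But the SAP does not say that they will be omitted, and its only rule that would govern them gives the wrong variance.

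A reader might also infer that the lesion rates carry the trial's claim of a systemic effect, or that the phase 3 decision is exposed. The documents do not support this. Lesion response is an exploratory endpoint, SAP 10.5.2.1 names subject-level iORR as the main efficacy endpoint for the phase 3 decision, and SAP Section 11 records that the sponsor had already decided not to proceed to phase 3. No test or threshold uses a lesion-level interval.

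The size of the effect is also open to challenge. The ICC and lesion counts are assumptions, and at ICC 0.1 the loss is small. The cap of 10 covers injected and uninjected lesions together, so it should not be read as 10 per set. Subjects with no lesion in a set drop out of it, so fewer than 27 may contribute. Finally, the planned lesion-count distribution and subject-level incidence let a reader see the clustering. These points limit the importance of the issue; they do not make the default interval valid.

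**Conclusion.** The point holds in conditional form. If lesion-level intervals for L-ORR, L-PR and L-CR are produced under SAP 9.6 and 10.1, they ignore within-subject correlation and are too narrow whenever the ICC is positive and subjects contribute more than one lesion to a set. Under the assumptions shown (27 subjects, a 25% rate, 3 lesions each), nominal 95% coverage falls to between about 0.92 and 0.82 over ICC 0.1 to 0.5. If only point estimates are reported, no interval is wrong. This is more than a missing detail, because following the stated rule gives incorrect error bars, but the consequence is low for an exploratory, descriptive endpoint with a subject-level summary beside it.

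**What to change.** In SAP 10.5.3.1, override the 10.1 default with one sentence: any interval for a lesion-level rate will be computed by resampling subjects (cluster bootstrap) or with a cluster-robust or GEE variance. Given about 27 subjects, a t reference for the robust interval is sensible. Alternatively, state that lesion-level rates carry no interval and that intervals are given only for the subject-level incidence of lesion response.

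The cost is a few lines of code and wider intervals: in the example, a half-width of 10.3 to 13.3 points in place of 9.4. No new data are needed and no other analysis changes.
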